2.4.2 Secondary

Assessed at 34 weeks postmenstrual age

- Survival
- Surgical NEC
- Spontaneous Intestinal Perforation

Assessed at 36 weeks postmenstrual age

- Bronchopulmonary dysplasia

Assessed at postnatal age 28 days

- Survival

Assessed at neonatal unit discharge (or death)

- Survival
- Surgery for NEC or NEC related condition after 34 weeks postmenstrual age
- Medical NEC
- Age in days to achieve an enteral intake of 150 ml/kg/day
- Treated retinopathy of prematurity

Title: COLLABORATE	EDGE No: 181495	Sponsor: Imperial College London	Version: 3.0; 09/01/2026
---------------------------	---------------------------	--	---------------------------------

- Severe brain injury
- Any diagnosis of milk-curd obstruction
- Length of neonatal unit stay
- Number of episodes of bacterial or fungal bloodstream infection
- Number of episodes of bacterial or fungal cerebrospinal fluid infection
- Number of episodes of bacterial or fungal urinary tract infection
- Number of days of antibiotic treatment
- Number of days on parenteral nutrition
- Number of days nil by mouth
- Weight, length, and head circumference Z-scores
- Change from birth in Z-scores for weight, length, and head circumference
- Any breast feeding (suckling at breast)
- Exclusive breast feeding (suckling at breast)
- Receiving any expressed Own Mother's Milk
- Receiving exclusive expressed Own Mother's Milk
- Maximum serum urea, creatine, and alkaline phosphatase
- Health resource use

Assessed at neonatal unit discharge (or death) in babies with NEC surgery

- Drain insertion prior to surgery (yes/no)
- Diagnosis of short bowel syndrome (yes/no)
- Diagnosis of intestinal failure-associated liver disease (yes/no)
- Length of bowel resected (cm)
- Primary surgical procedure (ileostomy; colostomy; end-to-end anastomosis)
- Number of re-operations (excluding primary operation)

Assessed at age 2-years corrected for prematurity

- Survival without moderate-severe cognitive-language impairment
- Survival
- Moderate-severe cognitive-language impairment
- Cognitive sub-score
- Language sub-score
- Gross motor function
- Hearing impairment
- Vision impairment

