6.8 Adverse reaction reporting

The use of pHDM, Preterm Formula and fortifier are established in routine care. In this extremely preterm population, we anticipate frequent foreseeable AE, SAE and AR, and a mortality rate to discharge from neonatal care of around 10%. For these reasons, AE, SAE, and AR will not be recorded.

All expected SAR have been listed as study endpoints, hence these events will be excluded from safety reporting. Any other SAR will be **unexpected** and extremely rare. These **unexpected** events will be reported to the Sponsor and Ethics Committee within 15 days of the investigator becoming aware of the event.

Cumulative data for safety endpoints (including expected SAR) will be included in regular safety reports reviewed by the Data Monitoring and Ethics Committee in accordance with the charter. Due to the established use of all trial interventions, additional safety oversight of expected events is not required.

Reporting of unexpected SAR will be performed through the eCRF. Unexpected SAR should be reported within 24 hours of the site study team becoming aware of the event as serious, unexpected and related (as described in section 6.4 and 6.6). SAR will be reported to the Sponsor's delegate (ICTU). Further details can be found in the safety reporting manual.

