7 STATISTICAL ANALYSES

7.1 Statistical Analysis Plan

We will construct a detailed Statistical Analysis Plan, signed off by the Chief Investigators and Trial Steering Committee prior to the first interim analysis. We will summarise baseline characteristics by randomisation arm within each comparison using appropriate statistical measures (mean, standard deviation; median, interquartile range; frequencies; percentages). The flow of participants through both comparisons will be reported according to the CONSORT Extension for Adaptive Designs (32). We will target a treatment policy estimand to estimate the effect of each intervention as delivered in practice regardless of any events that occur post-randomisation. The efficacy and safety analyses for both randomisations will be based on the intention-to-treat population. Missing data is expected to be very low as this is retrieved from NNRD. It is specified in the Parent Information Leaflet that should they withdraw consent for their baby's participation, data already available in the NNRD will be utilised.

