7.3 Primary endpoint analysis

We will model the main intervention effect for each randomisation separately. For both, we will use a binomial Generalized Estimating Equation (GEE) model with identity link and a log link function to estimate adjusted risk difference and adjusted risk ratio (in line with CONSORT reporting recommendations) with robust variance. This will enable us to account for within network correlations. Intervention effect for the first and second randomisation will be modelled separately. Both models will be adjusted for minimisation variables.

The analysis model for randomisation 1 will include whether or not an infant received fortification (Y/N) and whether or not they were randomised to this (randomisation 2; Y/N)). Though randomisation 2 will occur after randomisation 1, they are close in time and receiving fortification may be more likely to be a predictor of the primary outcome than a result of taking part in randomisation 1. Therefore, randomisation 2 and receipt of fortification will be treated as baseline covariates.

The analysis model for randomisation 2 will include adjustment for taking part in randomisation 1 (Y/N) and type of supplementary feed received (pHDM or formula). A supplementary analysis for randomisation 2 will be performed to determine the effect of rescue fortification in the standard of care arm (no routine fortification) will be undertake using principal stratum and complier average causal effect approaches (no rescue fortification is defined as a complier in the standard of care arm). In the unlikely case that missing data are greater than 2%, a sensitivity analysis will be performed using multiple imputation.

Title: COLLABORATE	EDGE No: 181495	Sponsor: Imperial College London	Version: 3.0; 09/01/2026
---------------------------	---------------------------	--	---------------------------------

Binary secondary and key safety outcomes (death, surgical NEC, medical NEC, infection) will be analysed using the same principled approach as the primary outcome. The age 2-year PARCA-R will also be evaluated as a continuous outcome and the between arm mean difference estimated using the GEE model with normal distribution and identity link function adjusting for minimisation variables.

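### The treatment-policy estimand cannot cover death for the 2-year PARCA-R scores, so the planned mean difference is a survivor-only comparison that is biased if a feed changes survival

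*Protocol*

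**What the plan says.** Section 7.1 targets a "treatment policy estimand to estimate the effect of each intervention as delivered in practice regardless of any events that occur post-randomisation". It names no other strategy for any event. The next sentence fixes the population: "The efficacy and safety analyses for both randomisations will be based on the intention-to-treat population".

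Section 7.3 gives binary secondary outcomes the primary-outcome approach. It then adds the continuous 2-year score: "The age 2-year PARCA-R will also be evaluated as a continuous outcome and the between arm mean difference estimated using the GEE model", with a normal distribution, an identity link and adjustment for the minimisation variables. It does not say how children who died before 2 years enter that model. The same section plans multiple imputation as a sensitivity analysis if missing data exceed 2%, without separating deaths from missing values.

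Section 2.4.2 lists "Survival without moderate-severe cognitive-language impairment" and survival among the 2-year endpoints. It also lists, as separate endpoints, "moderate-severe cognitive-language impairment" on its own and the cognitive and language sub-scores. Section 6.8 anticipates "a mortality rate to discharge from neonatal care of around 10" per cent.

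**The concern.** A treatment-policy strategy uses the outcome value whatever happens after randomisation. For a PARCA-R score after death there is no value to use. The rule in 7.1 therefore cannot hold for this outcome, and what remains is a comparison of survivors. Impairment taken alone and the two sub-scores have the same gap.

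Survivor groups stay comparable only if the feed leaves survival unchanged or the extra survivors resemble the rest. The hypotheses in 1.3.1 are that each intervention improves survival without surgical NEC. The observational analysis in 1.5.3 reports 15.1 points for that outcome with fortified feeds but only 1.4 points for surgical NEC. So 15.1 - 1.4 = 13.7 points are deaths without surgical NEC. The protocol says this may be residual confounding, so it is not a forecast. It does show that unequal survival is within the range the trial was set up to examine.

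Neurodevelopmental harm is the stated safety concern for both interventions (1.5.2 and 1.5.3). Section 7.9 also makes the long-term economic model conditional on better 2-year cognitive-language outcomes, without saying which analysis decides that.

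**Working it through.** **The plan's own figures.** The protocol gives no power or error figure for PARCA-R. Its stated minimum of 87% power is for the primary outcome (0.82 v 0.87). With the stated boundaries of 2.863, 2.337 and 2.024, that recomputes to about 88% at 1062 per arm, so the sample size is a sound input here.

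**Inputs from the protocol**
- 1084 per arm less 2% missing: 1084 x 0.98 = 1062 (7.2.1).
- For randomisation 1, the table in 7.4 gives 1908 at full recruitment: 1908 / 2 = 954 per arm.
- Mortality around 10% (6.8), so survival is placed near 0.90.
- The 5-point MCID (7.2.1) is for survival without surgical NEC. It is used only as the extreme in which all 5 points are deaths prevented.

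**Assumptions not in the protocol**
- No effect of the feed on the score of any child who would survive in either arm.
- Every child who survives in the worse arm would also survive in the better arm.
- Extra survivors score g SD lower, with g from 0.5 to 2.
- Questionnaire return of 60 to 100%, unrelated to the score.
- No credit for covariate adjustment.

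**Formulas** (scores in SD units, survival S0 < S1, return r, n per arm)
- Share of extra survivors: f = (S1 - S0) / S1
- Bias in the survivor mean: b = f x g
- Variance in the better-surviving arm: v = 1 + f(1 - f)g²
- SE = sqrt(1/(n S0 r) + v/(n S1 r))
- Two-sided rejection = Φ(b/SE - 1.96) + Φ(-b/SE - 1.96)

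**Worked case:** S0 = 0.88, S1 = 0.93, g = 1, n = 1062, r = 1.
- f = 0.05 / 0.93 = 0.0538, so b = 0.054 SD.
- v = 1 + 0.0538 x 0.9462 = 1.051.
- Scored survivors: 1062 x 0.88 = 934.6 and 1062 x 0.93 = 987.7.
- SE = sqrt(1/934.6 + 1.051/987.7) = 0.0462, so b/SE = 1.16.
- Rejection = 21.4%. At 80% return it is 18.0%, and at 60% return 14.7%.

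**Results** (nominal 5%)

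| Survival | Gain | g (SD) | n per arm | Bias (SD) | Rejection, 60-100% return |
|---|---|---|---|---|---|
| 0.89 v 0.91 | 2 points | 1 | 1062 | 0.022 | 6.6-7.7% |
| 0.885 v 0.915 | 3 points | 1 | 1062 | 0.033 | 8.5-11.0% |
| 0.88 v 0.93 | 5 points | 0.5 | 1062 | 0.027 | 7.4-9.0% |
| 0.88 v 0.93 | 5 points | 1 | 1062 | 0.054 | 14.7-21.4% |
| 0.88 v 0.93 | 5 points | 1 | 954 | 0.054 | 13.7-19.7% |
| 0.88 v 0.93 | 5 points | 1.5 | 1062 | 0.081 | 26.6-40.5% |
| 0.88 v 0.93 | 5 points | 2 | 1062 | 0.108 | 41.4-61.3% |

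Centring survival on 10% mortality (0.875 v 0.925, g = 1, n = 1062) gives almost the same: 14.8 to 21.5%. With equal survival and no selection on death, the bias is zero. Nearly all the excess rejection is in the direction of apparent harm from the feed that saves lives. If the feed increases deaths, the sign reverses.

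**The case against.** - **The death-inclusive endpoints already exist.** The composite comes first among the 2-year endpoints, 2-year survival is listed beside it, and 7.3 introduces the continuous analysis as additional. No alpha or stopping rule depends on it. This stands and limits the damage. It does not repair the estimand for the score, and nothing in the protocol says that the score must be read beside the composite.
- **The mean difference is adjusted.** Gestational age class, growth restriction and network are in the model and remove part of the selection. That also stands. Gestation enters only as below 26 weeks or not (5.3.2), so differences in frailty within strata can remain.
- **The 5-point gain is borrowed from another endpoint.** Correct. No document gives an expected survival difference at 2 years or a score deficit for the extra survivors. At 2 to 3 points the inflation is small.
- **This belongs in the SAP.** Detail on handling deaths often does. But the protocol itself states a strategy without exception, and that strategy cannot be applied to this outcome.
- **Ranking death as the worst score has its own flaw.** A feed that only saves lives would then look better on the ranked score, and the analysis largely repeats the composite. This is why it is only optional below.

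A reader might infer that a life-saving feed will test as harmful to cognition. The figures do not support that. In the 5-point, 1 SD case at 1062 per arm, 79 to 85% of trials would not reject.

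**Conclusion.** The point holds in limited form. Treatment policy as stated in 7.1 cannot apply to the PARCA-R scores or to impairment alone. Followed as written, the plan yields a survivor comparison that is biased whenever a feed changes survival and the extra survivors differ from the rest.

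With a 1 SD deficit and 1062 per arm, the false-positive rate rises from 5% to about 7-8% for a 2-point survival gain, 9-11% for 3 points and 15-21% in the 5-point extreme (14-20% at 954 per arm). A significant false harm becomes more likely than not only if all 5 points are deaths prevented, the extra survivors score about 2 SD lower and questionnaire return is high. The deficit, the return rate and the survival gain are all assumptions, and adjustment may lower these figures. The matter deserves correction because cognition is the named safety question. It does not touch the primary analysis.

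**What to change.** Amend 7.1 and 7.3 to state that:

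1. the treatment-policy strategy does not cover death for the PARCA-R score, its cognitive and language sub-scores, or impairment taken alone;
2. these are comparisons among survivors, to be interpreted only beside 2-year survival and the composite, and the composite carries the conclusion on cognition;
3. deaths are not treated as missing and are not multiply imputed;
4. a survivor-average-causal-effect (principal stratum) sensitivity analysis with bounds will be reported. The protocol already uses a principal-stratum approach for rescue fortification, so this adds no new framework.

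A ranked analysis of the score with death as the worst value may be added but is not needed.

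The cost is a few sentences, one further analysis on data already collected, and a more cautious reading of the score difference.

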7.4 Interim assessment of efficacy

We will conduct two pre-planned formal interim efficacy analyses when 50% and 75% of participants reach 34 weeks gestational age (i.e., primary outcome is available). This analysis will be undertaken by an independent ICTU statistician. Recruitment will continue during interim analyses. The analysis will employ two-sided O'Brien-Fleming efficacy boundaries. Unadjusted between arm differences in proportions will be calculated using the primary analysis models described for the final analysis. An identify link function will be used to obtain adjusted risk differences and corresponding Z-scores. Superiority will be assessed at each stage based on the critical value thresholds (Z-scores) and numbers of participants.

Proportion recruited	50%	75%	100%
Randomisation 1, n	954	1431	1908
Randomisation 2, n	1063	1594	2126
Critical value thresholds (Z-scale)	2.863	2.337	2.024

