7.2 Sample size and power

7.2.1 Main study

This is a group-sequential trial with 2 interim and 1 final analysis (i.e., an adaptive trial), hence the sample size is not fixed. The maximum sample size is 3252, (n=2168 in each randomisation; n=1084 per arm) assuming no early stopping, estimated on the composite primary efficacy outcome (survival to 34 weeks gestational age without surgical NEC (Y/N)).

Title: COLLABORATE	EDGE No: 181495	Sponsor: Imperial College London	Version: 3.0; 09/01/2026
---------------------------	---------------------------	--	---------------------------------

For the randomisation 1 (pHDM vs Formula supplement) an observational analysis of NNRD data estimated the difference in the proportion surviving to 34w PMA for babies born <29 weeks' gestation to vary between 0.18 and 0.52 depending on week of gestational age (favouring supplementation with preterm formula) (6) For the sample size calculation we targeted a highly conservative MCID in this proportion of 0.05 based on a baseline of 0.82 which we accurately estimated from the NNRD for this population of babies in the UK (i.e. from 0.82 to 0.87).

For randomisation, 2 (fortifier vs no routine fortifier) an unpublished observational analysis from NNRD data estimated the difference in proportion data surviving to 34w PMA for babies born <29 weeks gestation to vary between 0.06 and 0.75 depending on week of gestational age (favouring fortifier). Taking a conservative approach and in line with the first comparison, we have chosen to target the same MCID of 0.05.

We have calculated power based on a fixed sample size of 3252 unique babies using rpact (33) where interim timings were chosen to minimise the expected sample size. We anticipate at least 50% of babies will be co-enrolled into both randomisations. If co-enrolment is higher, power will increase. We have used an O'Brien & Fleming design with two-sided overall significance level of 5% to account for two interims at 50% and 75% and a normal approximation assumption for rates. For both randomisations we have factored in 2% missing outcome data due to carers withdrawing consent from routine data collection in NNRD.

Based on all the above assumptions, n=3252 (n=2168 in each randomisation and n= 1084 per arm) will achieve a minimum of 87% power for each randomisation. The expected sample size across for each randomisation is n=2439.

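### The randomisation 1 look sizes in section 7.4 (954/1431/1908) conflict with the 2168 babies, 2% loss and minimum 87% power planned in section 7.2.1

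*Protocol*

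**What the plan says.** Protocol section 7.2.1 sets a maximum of 3252 unique babies, "n=2168 in each randomisation; n=1084 per arm". On the effect size, "we targeted a highly conservative MCID in this proportion of 0.05 based on a baseline of 0.82", that is, 0.82 against 0.87. The design is a three-look O'Brien-Fleming plan, two-sided 5%, with interims at 50% and 75%. On missing data: "For both randomisations we have factored in 2% missing outcome data due to carers withdrawing consent from routine data collection in NNRD". The resulting claim is that "n=2168 in each randomisation and n= 1084 per arm) will achieve a minimum of 87% power for each randomisation".

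Section 7.4 then tabulates the looks:

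| | 50% | 75% | 100% |
|---|---|---|---|
| Randomisation 1, n | 954 | 1431 | 1908 |
| Randomisation 2, n | 1063 | 1594 | 2126 |
| Limit (Z) | 2.863 | 2.337 | 2.024 |

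The rule that uses the table is: "Superiority will be assessed at each stage based on the critical value thresholds (Z-scores) and numbers of participants". The same section says "Unadjusted between arm differences in proportions will be calculated using the primary analysis models described for the final analysis", and its next sentence takes the Z-scores from adjusted risk differences under an identity link.

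**The concern.** The two randomisations have the same planned size, the same loss allowance and the same power claim, so their rows in 7.4 should be identical. They are not: the final randomisation 1 count is 218 below that of randomisation 2 (2126 − 1908), and the protocol gives no reason.

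These counts time the looks that could stop the pHDM v formula comparison early, and they define its final analysis. A team working to 50% of the evaluable total and a team working to 954 would analyse at different times. Depending on which figure is meant, either the stated power or the stated type I error does not hold for randomisation 1.

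**Working it through.** **Inputs.** From 7.2.1: 2168 per randomisation, 1084 per arm, 2% missing, rates 0.82 and 0.87, two-sided 5%, looks at 50/75/100%. From 7.4: the counts and limits tabulated above.

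**Step 1. Which row fits the plan?**
- 2168 × 0.98 = 2124.6. Per arm, 1084 × 0.98 = 1062.3, rounded up to 1063, so 2126 in total. This is the randomisation 2 row.
- 1908/2168 = 0.880. Per arm, 1084 × 0.88 = 953.9, rounded up to 954, so 1908 in total. The randomisation 1 row is what a 12% deduction would give, but no 12% appears in the protocol.

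**Step 2. Are the limits right?** Under the null, the three Z-statistics are multivariate normal with correlation √(t_j/t_k). Solving for the classical O'Brien-Fleming constant at t = 0.5, 0.75, 1 gives c = 2.0242, and limits c/√t of 2.863, 2.337 and 2.024. Two-sided alpha is 0.0500. The printed limits are correct for looks at 50/75/100% of the final analysed number.

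**Step 3. Power.** With n analysed per arm, the drift is θ = 0.05/√(0.2607/n), where 0.2607 = 0.82 × 0.18 + 0.87 × 0.13 (unpooled variance). Each Z_k has mean θ√t_k. Power is one minus the probability that all three stay inside the limits.

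| Final analysed total | θ | Three-look power |
|---|---|---|
| 2125 to 2126 (2168 less 2%) | 3.19 | 88.4% |
| 1908 | 3.02 | 84.9% |

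The first line supports the protocol's minimum of 87% for 2168 with 2% loss. With pooled variance the figures are 88.3% and 84.7%. Solving for 87% power gives about 2031 analysed babies (2041 pooled).

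**Step 4. The two readings of the randomisation 1 row.**

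(a) *1908 is the final analysed number.* Then 954/1908 = 0.50 and 1431/1908 = 0.75. Looks and limits agree and alpha is 0.0500. Power is 84.9%, which is 2.1 points below the stated minimum.

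(b) *About 2125 are analysed, with looks at 954 and 1431.* Then 954/2125 = 0.449 and 1431/2125 = 0.673. The printed limits at 0.449/0.673/1 give a two-sided alpha of 0.0518 and power of 88.5%. If nobody is lost and 2168 are analysed, the fractions are 0.440 and 0.660, alpha is 0.0521 and power is 89.1%.

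**The case against.** **The effect is small.** Power is 2.1 points below the claim, or alpha is about 0.002 above 5%. The internal pilot in 7.10 treats power below 80% as its red line, and neither reading comes near it. Section 7.4 also gives the interim triggers in words, as 50% and 75% of participants, and the analysis plan is due before the first interim (7.1). This stands as an argument about severity. It does not remove the conflict between the two sections.

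**The 12% might have a clinical explanation.** Section 1.4 says that over 85% of extremely preterm babies need supplementary feeds, so a reader might take the shortfall to be babies who never needed one. The protocol does not support that. Under 5.3.1, randomisation 1 takes place only once a supplement is judged necessary, and 7.1 specifies intention-to-treat with a treatment policy estimand, so later non-use removes nobody.

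**Stronger readings that a reader might infer:**
- *The first look is early and power is also only 85%.* These exclude each other: 85% requires 1908 as the final number, which makes 954 exactly half.
- *The first look is at 44% of plan.* That divides a count net of losses by the gross 2168. Against the evaluable 2125 it is about 45%.
- *Power is lower still if the 5-point difference runs downwards from 0.82.* Section 7.2.1 and the trial summary both use 0.82 and 0.87, so this is not the plan's assumption.
- *The boundary statistic is undefined because 7.4 says 'Unadjusted'.* Section 7.4 attaches Z-scores only to the adjusted risk difference, and the sentence with 'Unadjusted' itself refers to the primary models, which 7.3 describes as adjusted. It is a stray word to delete.
- *The fixed O'Brien-Fleming limits are invalid, or the adjustment set must change.* Step 2 shows that the limits are exact at the stated fractions, and this mismatch does not bear on the choice of covariates.

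**Conclusion.** The randomisation 1 row in 7.4 cannot be reconciled with 7.2.1. One of two consequences applies: power of about 85% rather than at least 87%, with correctly timed looks; or looks at about 45% and 67% of the information, with alpha of about 0.052 and power of about 88%. The protocol does not show which is intended.

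The figures assume rates of 0.82 and 0.87, equal arms, the normal approximation, independent babies and the printed limits. The choice of variance moves power by about 0.2 points.

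This should be fixed. The size is modest and the design is not undermined, but the error lies in the stopping rule of one of the two primary comparisons.

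**What to change.** Before any comparative data are seen, do one of the following:

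- If 2% is the intended loss, set the randomisation 1 row in 7.4 to 1063/1594/2126. The printed limits and the 87% claim then hold.
- If a 12% loss is intended, give its reason in 7.2.1 and restate randomisation 1 power as about 85%. The row and limits can stay.

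In either case, if the looks will not fall at 50% and 75% of the final analysed number, recompute the limits at the actual fractions.

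Also delete 'Unadjusted' in 7.4, so that the boundary Z is clearly the one from the identity-link adjusted risk difference.

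The cost is a text correction to the protocol, carried into the analysis plan, and a slightly lower stated power if the 12% is real.

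### The overall two-sided 5% is not guaranteed: the O'Brien-Fleming limits are fixed for looks at 50/75/100%, but each comparison's final size can move with co-enrolment

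*Protocol*

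**What the plan says.** Section 7.2.1 describes a group-sequential design with two interim analyses and a final one, at a two-sided overall level of 5%. The quantity it holds constant is the number of distinct infants: "We have calculated power based on a fixed sample size of 3252 unique babies". It plans 2168 per randomisation on the basis of at least 50% co-enrolment and adds: "If co-enrolment is higher, power will increase".

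Section 7.4 says "The analysis will employ two-sided O'Brien-Fleming efficacy boundaries" and times the interim looks "when 50% and 75% of participants reach 34 weeks gestational age (i.e., primary outcome is available". Its table gives counts of 954, 1431 and 1908 for randomisation 1 and 1063, 1594 and 2126 for randomisation 2. A single row of limits serves both: 2.863, 2.337 and 2.024. The decision rule is "Superiority will be assessed at each stage based on the critical value thresholds (Z-scores) and numbers of participants".

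Neither section names a spending function or says that limits will be recomputed if the fractions differ from plan. Section 7.10 treats co-enrolment as uncertain: below 30% is red, above 50% is green, and there is no upper bound.

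**The concern.** Group-sequential limits depend on the fraction of the final information available at each look. Section 7.4 closes both the limits and the counts. Section 7.2.1 leaves the final size of each comparison open, because power can rise with co-enrolment only if the comparisons become larger. The denominator of the information fraction is then unknown when an interim look is taken.

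If co-enrolment exceeds plan and the looks stay at the printed counts, the looks come early on the information scale but use limits meant for later looks, and overall alpha exceeds 5%. If co-enrolment falls short, the looks come late and the procedure is conservative. The protocol's own expectation of at least 50% points towards inflation. At stake is the stated error rate of a trial that section 7.9 expects to be viewed as definitive.

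**Working it through.** **Inputs.** From section 7.2.1: 3252 unique babies, 2168 per randomisation, 50% co-enrolment, 2% missing outcome, two-sided 5%. From section 7.4: the limits and counts given above.

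**Reproducing the plan's limits.** Classic O'Brien-Fleming limits have the form C/√t. Solving for two-sided 5% at t = 0.5, 0.75 and 1 gives C = 2.0242, hence 2.0242/√0.5 = 2.863, 2.0242/√0.75 = 2.337 and 2.024. These are the printed limits, and overall alpha at those fractions is 5.00%.

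**Size of each comparison.** Let c be the co-enrolled share of each comparison. With N babies in each, the number of unique babies is 2N − cN, so N = 3252/(2 − c). At c = 0.5, N = 3252/1.5 = 2168, as stated. After 2% loss, 0.98 × 2168 = 2125, which matches the printed 2126 for randomisation 2.

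**Holding the printed limits and interim counts, letting N float (randomisation 2).** The fractions are t1 = 1063/(0.98N) and t2 = 1594/(0.98N). Under the null hypothesis the three Z statistics are multivariate normal with correlations √(ti/tj), and alpha = 1 − P(|Z1| < 2.863, |Z2| < 2.337, |Z3| < 2.024). Information is taken as proportional to the number of babies with the outcome.

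| c | N | N with outcome | t1 / t2 | overall alpha | final limit restoring 5%* |
|---|---|---|---|---|---|
| 0.3 | 1913 | 1875 | 0.567 / 0.850 | 4.74% | 1.996 |
| 0.5 | 2168 | 2125 | 0.500 / 0.750 | 5.00% | 2.024 |
| 0.7 | 2502 | 2452 | 0.434 / 0.650 | 5.23% | 2.051 |
| 0.8 | 2710 | 2656 | 0.400 / 0.600 | 5.34% | 2.063 |
| 1.0 | 3252 | 3187 | 0.334 / 0.500 | 5.53% | 2.086 |

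*With the printed interim limits kept.

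If co-enrolment is instead read as a share of unique babies, 50% gives 3252 × 1.5/2 = 2439 per comparison, and alpha at the printed randomisation 2 counts is 5.20%.

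**Randomisation 1.** Its printed final count, 1908, is 1908/2168 = 88% of the planned size. The stated 2% loss does not account for that. If randomisation 1 reaches about 2125 with outcome, looks at 954 and 1431 fall at 954/2125 = 44.9% and 1431/2125 = 67.3%. Alpha is then 5.18%, even at the planned co-enrolment.

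**The other readings.**
- Looks at 50% and 75% of all 3252 babies, with stable co-enrolment: the fractions stay at 0.50 and 0.75 in each comparison, and alpha is 5.00% at any co-enrolment level.
- The same, with drift: co-enrolment of 30% in the first half and 70% in the second gives N = 1626/1.7 + 1626/1.3 = 2207, fractions 0.433 and 0.717, and alpha 5.11%. The reverse order gives 4.89%.
- Each comparison ends at its printed final count: alpha is 5.00%.

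**The case against.** The strongest reply is that the plan as printed is correct. Its limits give exactly 5% at the planned fractions, and inflation needs three things together: co-enrolment above plan, looks held at the printed counts, and a final size that is allowed to grow. The timing sentence in section 7.4 is worded as a proportion, and two of the three readings above hold 5%. This stands, and it is why the conclusion is limited to the absence of a guarantee. A reader might infer that the 5% is breached outright; the documents do not support that.

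The excess is also small. The 5.5% figure needs every baby to enter both comparisons. Section 1.4 says over 85% of these infants need supplementary feeds, so some would never reach randomisation 1. That stands too.

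A reader might also infer that an earlier first look raises the chance of a false stop at that look. It does not: the two-sided tail beyond 2.863 is 0.42% at any information fraction. The excess arises because the statistics at the three looks are less correlated when the interim looks come earlier.

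Finally, section 7.1 promises a detailed SAP before the first interim analysis, and section 7.11 leaves stopping procedures to the DMEC charter. Recalculation rules often sit there, and their absence from a protocol would not alone be a fault. Here, however, the protocol itself commits to fixed thresholds and counts that do not fit its own floating sample size. A recalculation rule in the SAP would depart from section 7.4 unless that section is changed.

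**Conclusion.** The point holds in limited form: the stated two-sided 5% is not guaranteed. Sections 7.2.1 and 7.4 together leave open each comparison's final size and the denominator of the 50% and 75% triggers, while the limits are exact for one set of fractions only. Under the unfavourable reading, alpha runs from about 4.7% at 30% co-enrolment to 5.2-5.3% at 70-80%, with 5.5% as an extreme bound. The unexplained final count for randomisation 1 can by itself give about 5.2%.

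These figures assume that information is proportional to babies with the outcome, that co-enrolment is a share of each comparison, and that looks are taken at the printed counts. For randomisation 2 they use the stated 2% loss. Randomisation 1 gives the same alphas if its size scales in proportion to its printed counts. The effect is modest, but it bears on the stated error rate and should be settled before the first interim analysis.

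**What to change.** 1. State the planned maximum for each comparison, reconciling 2168 in section 7.2.1 with 1908 and 2126 in section 7.4. State whether the 50% and 75% triggers refer to all babies or to each comparison.
2. Specify for each comparison an O'Brien-Fleming-type (Lan-DeMets) alpha-spending function, or an equivalent recalculation of the limits, at the observed information fractions. Compute the final limit from the alpha already spent and the actual final number. At 70% co-enrolment, for example, this gives 3.208, 2.561 and 1.990, with overall alpha 5.00%.
3. Label the present table as illustrative at 50% co-enrolment.

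The cost is wording in section 7.4, the SAP and the DMEC charter. At exactly 50/75/100% the limits would move slightly, to about 2.96, 2.36 and 2.01: a little stricter at the interims and a little easier at the end, with negligible change in power. Recruitment and data collection are unaffected.
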